4.2.2. Total Number of Tablets Administered

The total number of tablets administered will be summarized using descriptive statistics.

The presumed total number of tablets administered to a participant will be determined by the data collected on the drug accountability CRF using the following formula:

Total Number of Tablets Administered =

$$\left(\sum$$
 No. of Tablets Dispensed $\right) - \left(\sum$ No. of Tablets Returned $\right)$

The maximum tablets administered is 10 tablets.

For missing number of tablets returned, imputation rules are described in programming specifications.

No formal statistical testing is planned.

A by-participant listing of study drug administration and drug accountability will be provided separately by participant ID number (in ascending order).

4.3. **Protocol Deviations**

Participants who did not meet the eligibility criteria for study entry but were enrolled in the study, will be summarized regardless of whether they were exempted by the sponsor or not. The summary will present the number and percentage of participants who did not meet at least 1 eligibility criterion and the number of participants who did not meet specific criteria by treatment group based on the All Randomized Analysis Set. A by-participant listing will be provided for all randomized participants who did not meet at least 1 eligibility (inclusion or exclusion) criterion. The listing will present the eligibility criterion (or criteria if more than 1 deviation) that participants did not meet and related comments, if collected.

Protocol deviations occurring after participants entered the study are documented during routine monitoring. The number and percentage of participants with important protocol deviations and the total number of important protocol deviations by deviation category (eg, eligibility criteria, informed consent) will be summarized by treatment group for the All Randomized Analysis Set. A by-participant listing will be provided for those participants with important protocol deviation.

4.4. Assessment of COVID-19 Impact

The study is in nonhospitalized participants with COVID-19; thus, no additional assessment of COVID-19 impact will be included.

5. **BASELINE CHARACTERISTICS**

5.1. Demographics and Baseline Characteristics

Participant demographic variables (eg, age, age group $[\ge 18 - < 65, \ge 65 - < 75, \ge 75 - < 85, \ge 85$ years], sex, race, and ethnicity) and baseline characteristics (eg, body weight, height, and body mass index [BMI]) will be summarized by treatment group and overall using descriptive statistics for continuous variables and using number and percentage of participants for categorical variables. The summary of demographic data and baseline characteristics will be provided for the Safety Analysis Set and FAPS.

For categorical data, the Cochran-Mantel-Haenszel (CMH) test (ie, general association statistic for nominal data and row mean scores for ordinal data) will be used to compare the 2 treatment groups. For continuous data, the 2-sided Wilcoxon rank sum test will be used to compare the 2 treatment groups.

Similar summaries will be provided for the following subgroups corresponding to randomization strata: duration of symptoms at enrollment (≤ 3 days versus > 3 days); vaccination status (ever versus never)

A by-participant demographic listing, including the informed consent date, will be provided by participant ID number in ascending order.

5.2. Other Baseline Characteristics

The following baseline disease characteristics will be summarized by treatment group and overall using descriptive statistics for continuous variables and using number and percentage of participants for categorical variables for the Safety Analysis Set and FAPS:

- Randomization strata: duration of symptoms at enrollment (≤ 3 days versus > 3 days); vaccination status (ever versus never)
- Duration of COVID-19 symptoms prior to first dose of study drug
- Duration from first positive SARS-CoV-2 diagnostic test to first dose of study drug
- Risk factors defined in the inclusion criteria
- Total number of risk factors
- Number of targeted COVID-19 symptoms at baseline measured via the SIC questionnaire
- Summary for each COVID-19 targeted symptom at baseline, where an answer "No" to the questions will be considered as 0 in the summary of severity rating

- Baseline seropositivity: overall positive, ie, anti-spike antibody positive or anti-nucleocapsid antibody positive, versus overall negative, ie, both anti-spike antibody and anti-nucleocapsid antibody negative
- Baseline respiratory viral coinfections: None; Yes subdivided into: Influenza A; Influenza B; respiratory syncytial virus (RSV)
- Baseline SARS-CoV-2 viral load (as a continuous variable, and a categorical variable with $< 6 \log_{10} \text{ copies/mL versus} \ge 6 \log_{10} \text{ copies/mL})$
- Baseline eGFR: Creatinine Clearance by Cockcroft-Gault: \ge 90 mL/min, \ge 60–< 90 mL/min, \ge 30 < 60 mL/min, < 30 mL/min

For categorical data, the CMH test (ie, general association statistic for nominal data and row mean scores for ordinal data) will be used to compare the 2 treatment groups. For continuous data, the 2-sided Wilcoxon rank sum test will be used to compare the 2 treatment groups.

Similar summaries (except randomization strata) will be provided for the following subgroups corresponding to randomization strata: duration of symptoms at enrollment (\leq 3 days versus > 3 days); vaccination status (ever versus never).

A by-participant listing of other baseline characteristics will be provided by participant ID number in ascending order.

5.3. Medical History

Any medical condition or clinically significant laboratory abnormality with an onset date before the consent form is signed, or before the first dose of study drug and not related to a protocol-associated procedure is considered to be preexisting and should be documented as medical history. General medical history data will be collected at screening. It will be coded using the current version of Medical Dictionary for Regulatory Activities (MedDRA). A summary table will present the percentages of participants reporting each medical history preferred term, sorted first in alphabetical order by system organ class (SOC) and then by preferred term (PT) in descending order of total frequency within SOC. In addition, medical history will also be summarized by PT only, in descending order of total frequency.

6. EFFICACY ANALYSES

6.1. Primary Efficacy Endpoint

6.1.1. Definition of the Primary Efficacy Endpoint

The primary endpoint of the study is the proportion of COVID-19–related hospitalization or all-cause death by Day 29. The endpoint will be derived by combining the available all-cause death and COVID-19–related hospitalization reported by the site.

COVID-19–related hospitalization is defined as \geq 24 hours of acute care for a reason related to COVID-19, in a hospital or similar acute care facility, including emergency rooms or temporary facilities instituted to address medical needs of those with COVID-19. This includes specialized acute medical care units within an assisted living facility or nursing home. This does not include hospitalization for the purposes of public health and/or clinical study execution. The date and duration of hospital admission, and primary reason for hospitalization (including if the hospitalization is related to COVID-19) will be recorded.

6.1.2. Statistical Hypothesis for the Primary Efficacy Endpoint

Null hypothesis: The hazard ratio of COVID-19–related hospitalization or all-cause death by Day 29 between the 2 treatment groups is equal to 1.

Alternative hypothesis: The hazard ratio of COVID-19–related hospitalization or all-cause death by Day 29 between the 2 treatment groups is not equal to 1.

6.1.3. Primary Analysis of the Primary Efficacy Endpoint

The FAPS will be used for the primary efficacy endpoint analysis.

The hazard ratio of COVID-19–related hospitalization or all-cause death by Day 29 between the 2 treatment groups will be estimated using a Cox proportional hazards model with the stratification factors (duration of symptoms and vaccination status) as covariates. The hazard ratio, p-value, 95% confidence interval (CI) for the hazard ratio from the Cox model, and proportion of COVID-19-related hospitalization or all-cause death at Day 29 from the Kaplan-Meier estimate will be provided. In addition, the p-value from stratified log rank test will be provided. If 5 events or fewer across both treatment groups are observed within 1 or more stratum, the primary endpoint will be evaluated in the same analysis described above without using the corresponding stratification factor(s) as covariates.

If a participant prematurely discontinues from the study prior to Day 29 and prior to COVID-19-related hospitalization and is alive by Day 29, or the hospitalization status is missing, the participant is censored at the Last Study Date or Day 29, whichever is earlier. If a participant prematurely discontinues from the study prior to Day 29 and prior to COVID-19-related hospitalization and then dies on or prior to Day 29, then date of the death and status will be used for the primary analysis for this participant. If a participant has a COVID-19–related

hospitalization first and then dies, then date of the COVID-19–related hospitalization and status will be used for the primary analysis for this participant. If a participant has a non COVID-19-related hospitalization first and then dies without experiencing a COVID-19-related hospitalization, then date of the death and status will be used for the primary analysis for this participant. Handling of intercurrent events is defined in Section 6.4.

The number and percentage of participants with COVID-19–related hospitalization or all-cause death by Day 29 will be summarized.

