1.2. Study Design

This Phase 3 study is a randomized, double-blind, placebo-controlled study comparing the safety and efficacy of oral GS-5245 with placebo in nonhospitalized participants with COVID-19 who are at high risk of progression to hospitalization.

Randomization will be stratified by duration of symptoms at enrollment (\leq 3 days versus > 3 days) and vaccination status (ever versus never).

An overview of the study design is shown in Figure 1.

Figure 1. Study Schema

COVID-19 = coronavirus disease 2019; D = Day

- a Access determined at the site level by the principal investigator and participant.
- b Effective COVID-19 antiviral therapies such as nirmatrelvir/ritonavir, molnupiravir, ensitrelvir, intravenous remdesivir, monoclonal antibodies, or any other locally authorized/approved direct-acting therapy against SARS-CoV-2.

Approximately 2300 participants were planned to be randomized into the study. After screening procedures, eligible participants are randomized in a 1:1 ratio to receive treatment with GS-5245 or placebo.

The schedule of study procedures is presented in Appendix 1.

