1.3. Sample Size and Power

A total sample size of approximately 2300 participants provides approximately 90% power to detect a ratio of 0.25 (GS-5245 to placebo) in the primary endpoint (proportion of COVID-19-related hospitalization or all-cause death by Day 29), which is equal to a hazard ratio of 0.25 using a 2-sided significance level of 0.05 assuming the placebo event rate is 2% in the placebo group. The estimate of 2% in the placebo group is based on the placebo event rate for COVID-19 in the EPIC-SR study {Pfizer Inc 2022} and vaccine efficacy data from the Centers for Disease Control and Prevention Morbidity and Mortality Weekly Report {Ferdinands 2022, Thompson 2022}.

The sample size calculation was performed using software East[®] (Version 6.5, module for log-rank test given accrual duration and study duration and 1 or 2 interim analyses using the Lan DeMets approach with O'Brien-Fleming type spending function, with sample size re-estimation).

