3.8. Analysis Visit Windows

3.8.1. Definition of Study Day

Study day will be calculated from the first dosing date of study drug and derived as follows:

- For assessment dates on or after the first dosing date: Assessment Date First Dosing Date + 1
- For days prior to the first dose: Assessment Date First Dosing Date

Therefore, Study Day 1 is the day of first dose of study drug administration.

Last Dose Date is defined as the maximum, nonmissing, nonzero dose end date of treatment recorded on the Study Drug Administration eCRF form with "Study Drug Permanently Withdrawn" box checked for participants who prematurely discontinued or completed study drug according to the Study Drug Completion eCRF. Refer to Section 4.2 for missing date imputation, if necessary.

Last Study Date is the latest of the study drug start dates and end dates, the in-person or virtual visit dates, the vital sign collection dates, the questionnaire collection dates, the laboratory collection dates, and the death date (if applicable, for participants who died during the study, the death date will be the Last Study Date. For participants who died after completing the study or after prematurely discontinuing the study, the death date will not be considered for the Last Study Date).

Baseline value is defined as the last value obtained on or prior to the first dose date unless otherwise specified (see Section 3.8.3).

3.8.2. **Analysis Visit Windows**

Participant visits might not occur on protocol-specified days. Therefore, for the purpose of analysis, observations will be assigned to analysis windows.

The analysis windows for vital signs are provided in Table 3-1.

Table 3-1.	Analysis Visit V	Vindows for	Vital Signs

		Visit Window Study Day	
Analysis Visit	Nominal Study Day	Lower Limit	Upper Limit
Baseline	1	(none)	1
Day 3	3	2	4*
Day 5	5	4*	7
Day 10	10	8	12
Day 15	15	13	22
Day 29	29	23	34

If the nominal visit is a scheduled visit and the assessment is done on Day 4 (ie, Study Day = 4), assign to Day 3 or Day 5 analysis window based on the nominal visit label. If the nominal visit is an unscheduled visit or early discontinuation visit on Day 4, assign to Day 3 analysis window.

The analysis windows for SARS-CoV-2 mid-turbinate nasal swab are provided in Table 3-2.

		Visit Window Study Day	
Analysis Visit	Nominal Study Day	Lower Limit	Upper Limit
Baseline	1	(none)	1
Day 3	3	2	4*
Day 5	5	4*	7
Day 10	10	8	12
Day 15	15	13	22

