6.2.1. Analysis of Secondary Efficacy Endpoints

The FAPS will be the primary analysis set for key secondary efficacy endpoints and time to COVID-19 symptom alleviation. The Virology Analysis Set will be the primary analysis set for SARS-CoV-2 nasal swab viral load.

The key secondary endpoints will be tested in the following sequential order using a gatekeeping approach:

- 1. Proportion of participants with all-cause hospitalization by Day 29
- 2. Proportion of participants with COVID-19-related MAVs or all-cause death by Day 29
- 3. Proportion of participants with COVID-19-related MAVs by Day 29
- 4. Proportion of participants with all-cause death by Day 29

The proportion of participants with all-cause hospitalization by Day 29, COVID-19–related MAVs or all-cause death by Day 29, COVID-19 related MAVs by Day 29, and all-cause death by Day 29 will be analyzed in a similar manner to the primary endpoint.

All-cause death by Day 29 will also be compared between the 2 treatment groups using the Fisher's exact test. If a participant prematurely discontinues from the study prior to Day 29 and the death status is missing, the participant will not be included in the analysis.

The Kaplan-Meier product limit method will be used to estimate, and stratified log-rank test will be used to compare the 2 treatment groups for the time to COVID-19 symptom alleviation by Day 15. In addition, a Cox proportional hazards regression model with the stratification factors as covariates will be used to estimate the hazard ratio and its 2-sided 95% CI.

Change from baseline in SARS-CoV-2 nasal swab viral load to each visit including Day 5 will be compared between the 2 treatment groups using a mixed-effects model repeated measures (MMRM) approach. Additionally, change in SARS-CoV-2 viral load from baseline at each postbaseline analysis visit will be provided. Descriptive statistics will be provided by treatment group as follows: (1) Baseline values, (2) Values at each postbaseline analysis visit, (3) Change from baseline at each postbaseline analysis visit. **CCI**

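### SAP 6.1.3 counts a death after early study exit but censors known survivors at exit, and gives no consistent rule for a hospitalization after exit

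*SAP*

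**What the plan says.** SAP 6.1.3 has two branches for a participant who leaves early without a prior COVID-19-related admission. The first covers anyone who leaves before Day 29 and before a COVID-19-related "hospitalization and is alive by Day 29, or the hospitalization status is missing, the participant is censored at the Last Study Date", or at Day 29 if that comes first. The second covers a participant who leaves in the same way and "then dies on or prior to Day 29, then date of the death and status will be used for the primary analysis". A further sentence says that when a COVID-19-related admission is followed by death, the admission date is used. It does not say whether the participant must still have been in the study.

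The Last Study Date in SAP 3.8.1 is built from dosing, visit, vital-sign, questionnaire and laboratory dates, plus a death during the study. Hospitalization dates are not listed. For a death after study completion or premature discontinuation, "the death date will not be considered for the Last Study Date".

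Other sections point a different way. SAP 3.6.1 censors participants whose primary outcome is missing because they left. SAP 6.1.1 says: "The endpoint will be derived by combining the available all-cause death and" the COVID-19-related hospitalizations that the site reports, with no on-study condition. Under SAP 6.2.1, "all-cause death by Day 29 will be analyzed in a similar manner to the primary endpoint"; the same holds for the hospitalization and MAV endpoints. That section adds a Fisher's exact test for death which drops only early leavers whose death status is missing.

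**The concern.** Censoring should not depend on what happens afterwards. Under 6.1.3, two participants who leave on the same day are followed for different lengths of time depending on whether they later die. The one known to be alive on Day 29 leaves the risk set at exit, while the one who dies stays in it until death. In the all-cause death analysis this affects the whole endpoint, and the accompanying Fisher test keeps the known survivors that the time-to-event analysis cuts off.

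For hospitalization the difficulty is the conflict between sections. Two programmers working from the same SAP could build different primary event datasets, one counting a recorded admission after exit and one censoring it. The trial expects few events. SAP 6.5 also drops the two missing-status analyses that protocol 8.5.1 allowed (multiple imputation, and missing taken as hospitalized), so no planned analysis of missing status would show how much depends on the choice.

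**Working it through.** **1. The rule applied to four paths.** The days are illustrative; each participant leaves on Day 6.

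| After exit | Handling |
|---|---|
| No admission, alive on Day 29 | Censored at Last Study Date, about Day 6 |
| No admission, dies Day 20 | Event on Day 20 |
| COVID-19 admission Day 9, alive on Day 29 | 6.1.3 read literally: censored about Day 6. 3.6.1 with 6.1.1: event on Day 9 |
| COVID-19 admission Day 9, dies Day 20 | Event on Day 20 by one sentence of 6.1.3, on Day 9 by another |

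Rows 1 and 2 show follow-up that depends on outcome and need no interpretation. Row 3 depends on the reading. Missing hospitalization status is a separate alternative in the sentence, so the alive-on-Day-29 branch is not confined to missing status. Row 4 is an overlap.

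**2. The plan's own figure.** From SAP 1.3: "A total sample size of approximately 2300 participants provides approximately 90% power to detect a ratio of 0.25 (GS-5245 to placebo"), "using a 2-sided significance level of 0.05 assuming the placebo event rate is 2% in the placebo group". From SAP 1.2: "eligible participants are randomized in a 1:1 ratio to receive treatment with GS-5245 or placebo", so 1150 per arm.

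- Expected events: 1150 × 0.02 + 1150 × 0.005 = 23 + 5.75 = 28.75.
- Freedman: z = √28.75 × (1 − 0.25)/(1 + 0.25) − 1.960 = 3.217 − 1.960 = 1.257, power 0.896.
- Two proportions: 0.900. Schoenfeld: 0.961.

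The stated power is reproduced and is not in dispute.

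**3. Events available.** SAP 2.3 says enrolment stopped below 50% of plan, so below 1150 participants. At planning rates 1150 participants give 28.75/2 = 14.4 events. The reason given for stopping was a lower-than-expected event rate, so the true number is probably smaller.

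**4. Events that could fall after exit.** The documents give no dropout rate, so I assume 2% to 10%. With exit and event times both uniform over 29 days, half of a leaver's events fall after exit. Affected events = total × dropout × 0.5. This treats every such event as a recorded hospitalization in a survivor, which is generous.

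| Dropout | Of 28.75 | Of 14.4 |
|---|---|---|
| 2% | 0.29 | 0.14 |
| 5% | 0.72 | 0.36 |
| 10% | 1.44 | 0.72 |

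If events come early (exponential, mean 7 days, truncated at 29), 10% dropout gives 0.65 and 0.32. At full size, losing 1.44 events lowers Freedman power from 0.896 to 0.880. As a stress case, take 10% dropout with five times the risk after exit, holding the total fixed: 28.75 × 0.10 × 0.5 × 5 = 7.19 events, power 0.796; at 1150 participants, 3.59 events. No passage supports that multiple.

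**5. Distortion of the Kaplan-Meier estimate.** This is a single-arm simulation of 2,000,000 participants with uniform event and exit days and 10% dropout unrelated to risk.

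| Hospitalization / death risk | True Day 29 risk | KM, literal rule | KM, all censored at exit | Crude proportion, literal rule |
|---|---|---|---|---|
| 1.8% / 0.2% | 1.996% | 2.007% | 1.995% | 1.907% |
| 1.0% / 1.0% | 1.980% | 2.031% | 1.976% | 1.930% |
| 0.45% / 0.05% | 0.493% | 0.496% | 0.494% | 0.471% |

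The crude proportion loses events, while the KM estimate is pushed slightly up. The excess is close to dropout × 0.5 × death risk: 0.10 × 0.5 × 0.2% = 0.010 points (simulated 0.011), and 0.10 × 0.5 × 1.0% = 0.050 points (simulated 0.051). With the same dropout and the same share of deaths in both arms, the risk ratio hardly moves: 0.493/1.996 = 0.247 true, 0.496/2.007 = 0.247 under the rule.

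**The case against.** A reader might infer that real primary events are being discarded. The documents do not establish that. Leaving before a COVID-19-related hospitalization can also mean leaving without having had one, and 3.6.1 and 6.1.1 both favour counting a recorded admission. Loss occurs only if 6.1.3 is programmed literally and such admissions are in the database. Neither is shown.

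The affected group may be empty or nearly so. Participants who stop study drug are to be kept in follow-up (protocol 3.3.1.1, 6.4). The listed reasons for leaving the study are withdrawn consent and death (3.3.1.2), and no further contact is required after loss to follow-up (3.3.3). No section plans active collection of hospitalizations after exit. They could still become known: inpatient admission is an SAE (7.1.2) and adverse events are collected to 30 days after the last dose (7.3.2).

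It is also tempting to argue that leavers are those getting worse. Protocol 3.3.1.1 makes worsening a reason to stop drug, not to leave the study, so this has no source. Likewise one can show a result changing. With z = (a − d/2)/√(d/4), where a is placebo events and d is all events, 12 versus 3 gives p = 0.020, 11 versus 3 gives 0.033 and 10 versus 3 gives 0.052. The arithmetic is right, but it needs two recorded admissions after exit, both in placebo survivors, at planning event rates. Step 4 gives about 0.7 in both arms together at 10% dropout and equal risk.

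Finally, Fisher's test is an additional binary analysis, so different data handling is not in itself an error, and SAP 6.5 reports a very low death rate. These objections limit the size. They do not remove the stated difference between deaths and known survivors, the overlap on event date, or the conflict between sections.

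**Conclusion.** The point stands as an inconsistency in the rule for outcomes after early exit. That deaths after exit are counted while known survivors are censored at exit is explicit in 6.1.3 and carries into the all-cause death analysis. That a survivor's recorded admission is censored holds only on the literal reading, which conflicts with 3.6.1 and 6.1.1. The double date for exit, admission, then death is a plain overlap.

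The expected size is small: under about 1 event at 1150 participants if dropout is at most 10% and risk after exit is unchanged, both assumed. The upward shift in the KM estimate is 0.01 to 0.05 percentage points for an arm at about 2% risk under the simulated assumptions. With no such cases there is no effect. A larger effect needs high dropout, much higher risk after exit or different exit patterns by arm, and the documents give no figure for any of these. It should still be settled, because few events are expected, the missing-status analyses are gone and the correction is cheap.

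**What to change.** In SAP 6.1.3, state three things:

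- Any COVID-19-related hospitalization meeting the Appendix 3 definition, or any death, recorded with onset on or before Day 29 is an event on the date of the first such event, whatever the study status.
- A leaver whose Day 29 status for that endpoint is known is followed to Day 29.
- Only leavers of unknown status are censored, at the last date their status for that endpoint is known.

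Apply the same rule to the hospitalization and MAV endpoints. For all-cause death, censor non-events at the date last known alive or Day 29, whichever is earlier. The second and third statements are essential: counting more events after exit while still censoring event-free leavers at exit would extend the same asymmetry to hospitalizations.

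Report the number of events after exit by arm. Because hospitalizations after exit reach the database only passively, add one sensitivity analysis censoring everyone at study exit.

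The cost is a few sentences, a small change to the event and censoring derivation, and one extra analysis, with no new data collection. Data after exit can be used only where consent and local law allow, which already applies to the deaths now counted. SAP section 1 provides for changes after finalization to be documented in the CSR.
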